5.0 TREATMENT PLAN

5.1 Administration of study agents.

This is an open-label, Phase I/II trial with a dose escalation phase. The primary objective of the dose escalation phase is to determine the recommended phase 2 dose (RP2D) of entospletinib in combination with obinutuzumab in patients with relapsed/refractory CLL and B-cell malignancies. The Phase II portion will further evaluate the efficacy and safety of this novel combination.

Treatment will be administered on an outpatient basis but will also be permitted inpatient.

Reported adverse events and potential risks associated with entospletinib and obinutuzumab are described in Section 7. Appropriate dose modifications for both drugs are described in Section 6. No investigational or commercial agents or therapies other than those described below may be administered with the intent to treat the participant's malignancy.

The timing of study assessments and procedures is presented by study cycle and day and are abbreviated by the following references: Cycle (C) and Day (D) number, as in C1D1 (Cycle 1 Day 1). Cycles and days within each week are numbered sequentially thereafter.

Entospletinib will be administered as single agent for 7 days (during the run-in phase (days -7 to -1) for the purpose of correlative studies, followed by a combination with obinutuzumab (beginning with C1D1). C1D1 will occur immediately after Day -1 of the run-on phase (i.e., there is no "day 0").

Table 1. Treatment description

Agent	Pre-medications; Precautions	Dose	Route	Schedule	Cycle Length
Entospletinib*	None	According to dose level- see below	PO	BID or daily on Days -7 to -1 (run-in phase), and then beginning with C1D1	
Obinutuzumab	Benadryl Tylenol Dexamethasone	3000 mg split dosing in cycle 1, 1000 mg with each subsequent cycle	IV	C1D1 – 100 mg C1D2 – 900 mg C1D8 & 15 – 1000 mg Day 1 of cycles 2-6 – 1000 mg	28 days (4 weeks)

* The morning dose of entospletinib will be administered in the clinic on day -7 of the run-in phase, and subsequent doses will be self-administered

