10.2 Treatment Period

Clinic visits will be performed every cycle on Day 1. Under certain circumstances (e.g., clinic holiday, inclement weather) Day 1 may be delayed by not more than 3 days or occur earlier than scheduled by not more than 3 days during cycles 2-12; Days 8 and 15 of Cycle 1 may be delayed by 1 day or occur 1 day early.

Clinical laboratory assessments are to be collected on D1 of each cycle visit, or \leq 48 hours before those visits, and the test results must be available and reviewed before obinutuzumab is given (C1-6). Screening assessment tests can be considered as Day -7 tests (start of treatment) if performed \leq 72 hours before the first dose of study treatment; otherwise, the required evaluations must be repeated within this timeframe.

On Day -7 and C1D1 all patients with CLL/SLL will provide samples for biomarker analysis.

After the initial 12 treatment cycles subjects in whom it is clinically safe to do so, are benefitting from entospletinib, and who desire to continue entospletinib monotherapy may continue entospletinib therapy beyond the initial twelve cycles, with approval from the treating physician and sponsor-investigator, until disease progression or removal from treatment (see Section 5.4).

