11.1 Disease Evaluations

Physical examination, which will focus on documenting a change in the number of sites and size of lymphadenopathy, hepatomegaly and splenomegaly, will be done as part of the full disease evaluation during treatment. More extensive physical exams will be performed if guided by the development of new symptoms.

Complete blood count (CBC) with measurement of parameters including ALC will be obtained before start of treatment (Day -7), Days 1, 2, 8 and 15 of C1; on day 1 for the remaining twelve cycles, every 3 months for the first 12 months, and every 4-6 months thereafter until disease progression or death.

Serum biochemistry/metabolic panel will be obtained on will be obtained on Days -7, 1, 2, 8 and 15 of C1; on day 1 for the remaining twelve cycles, every 3 months for the first 12 months, and every 4-6 months thereafter until disease progression or death.

Computed tomography (CT) scan of neck, chest, abdomen and pelvis with intravenous contrast where possible will be performed at screening, on C4D1, C7D1, C10D1 (or ≤ 72 hours prior), at C18D1 and C24D1 should patients opt to continue Entospletinib monotherapy

A unilateral bone marrow aspirate and biopsy must be obtained during screening or up to 6 months before the first dose of study drug. Subjects who have bone marrow aspirate and biopsy results since completion of their last therapy for CLL may use those results if they were obtained within 6 months prior to the first dose of study drug. If the subject's physical examination findings, laboratory and radiographic evaluations suggest that CR has been obtained during C7D1, a bone marrow aspirate/biopsy should be obtained to confirm the CR within the timeframe specified above.

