- Reduction in lymphadenopathy by physical examination or by imaging as defined by:
 - A decrease in lymph node size by 50% or more either in the sum products of up to 6 lymph nodes, or in the largest diameter of the enlarged lymph node(s) detected prior to therapy
 - No increase in any lymph node, and no new enlarged lymph node
 - In small lymph nodes (< 2 cm), an increase of less than 25% is not considered significant
- A reduction in splenomegaly and hepatomegaly by 50% or more, by physical examination or imaging.

PR with Lymphocytosis

Because of the expected egress of CLL cells into the peripheral blood with BCRi, lymphocytosis may be encountered with entospletinib. Therefore progressive lymphocytosis without other clinical evidence of disease progression cannot be used to define disease progression. Accordingly, lymphocyte count will be ignored in the evaluations of progression. Of note, this has been an accepted standard in trials using inhibitors of B-cell receptor signaling for the treatment of CLL.

Furthermore, lymphocytosis should not interfere at the time of designation of a PR. PR with lymphocytosis should be based on other measurable aspects of disease other than ALC [45].

Progressive Disease

Includes at least one of the following:

- Appearance of any new lesion, such as enlarged lymph nodes > 1.5 cm, splenomegaly, hepatosplenomegaly, or other organ infiltrates.
- An increase by 50% or more in greatest determined diameter of any previous site including, liver and/or spleen,
- A 50% or greater increase in lymphocyte count.
- Transformation to a more aggressive histology (eg, Richter syndrome). Whenever possible this diagnosis should be established by lymph node biopsy.

Progressive Disease After Treatment

Includes at least one of the following:

- Any progressive disease criteria listed above
- The progression of any cytopenia (unrelated to autoimmune cytopenia) which occurs at least 3 months after treatment as documented by:
 - a decrease in Hb levels by more than 20 g/L (2 g/dL) or to less than 100 g/L (10 g/dL), OR
 - a decrease of platelet counts by more than 500,
- OR
- a decrease of platelet counts by more than 50% or to less than $100 \times 10^9/L$ ($100\,000/\mu L$).

Stable Disease

Patient who have not achieved a CR or a PR, and who have not exhibited progressive disease, will be considered to have stable disease (which is equivalent to a nonresponse).

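### Section 11.2.1 says lymphocyte count is to be ignored when judging progression in CLL/SLL, then lists an unqualified 50% lymphocyte rise as enough to call progressive disease

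*Combined protocol and SAP*

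**What the plan says.** Three parts of section 11.2.1, which covers CLL/SLL only, bear on this.

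- **PR with Lymphocytosis.** The reason is given first: "Because of the expected egress of CLL cells into the peripheral blood with BCRi, lymphocytosis may be encountered with entospletinib". The rule follows: "progressive lymphocytosis without other clinical evidence of disease progression cannot be used to define disease progression". It is then restated without any condition: "Accordingly, lymphocyte count will be ignored in the evaluations of progression". A separate sentence extends the idea to the designation of PR.
- **Progressive Disease.** Any single item on the list is sufficient. The items are new lesions, growth of a previous site by half or more, transformation, and "A 50% or greater increase in lymphocyte count". The lymphocyte item carries no exception for time on drug and no reference back to the paragraph above it.
- **Progressive Disease After Treatment.** Its first item is "Any progressive disease criteria listed above", which brings the lymphocyte item in unchanged.

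On timing, section 5.1 provides a run-in: "Entospletinib will be administered as single agent for 7 days", before the first obinutuzumab dose. Section 11.1 schedules blood counts before treatment on Day -7 and then on "Days 1, 2, 8 and 15 of C1; on day 1 for the remaining twelve cycles". Disease progression is a reason to stop treatment in section 5.4 and to come off study in section 5.6.

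**The concern.** The section contains two rules for the same finding, and they give opposite answers. The protocol expects lymphocytes to move into the blood under this drug class and says why that is not progression. An assessor who works from the Progressive Disease list, which is where one would look to decide whether a patient has progressed, would nonetheless record progression.

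For the patient, the stake is removal from a treatment that may be working. For the analysis, it is a progression status that depends on which part of the section the assessor relied on. Section 4.0 provides for participating sites besides the coordinating centre, so different assessors could rely on different parts.

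**Working it through.** No figure in the plan rests on this point, so there is nothing to reproduce. The check is to apply both rules to the same patient.

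**Step 1: classification.** Take a CLL/SLL patient with a lymphocyte rise of 50% or more, no new lesion, no growth of a previous site by half or more, and no transformation.

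| Situation | PR with Lymphocytosis paragraph | Progressive Disease lists |
|---|---|---|
| On entospletinib, nodes and spleen not meeting PR | Not progression | Progression (one item met) |
| On entospletinib, otherwise meeting PR | PR with lymphocytosis | Progression (one item met) |
| After entospletinib has stopped | Count ignored; no time limit stated | Progression (item imported) |

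The rules disagree in every row. In the first two, the list gives the answer the protocol itself rejects. In the third, the paragraph is the doubtful one: its reason, cell egress on drug, no longer applies, yet its last sentence would still set aside a relapse seen only in the blood. No other section of the document reconciles the two.

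**Step 2: when the conflict could arise.** Entospletinib is given alone on Days -7 to -1, which is 7 days. Table 8 schedules a count on Day -7 and another on C1D1, and section 10.2 requires Day 1 results to be reviewed before obinutuzumab is given. Taking the Day -7 count L as the reference (my assumption, for illustration), the item is met at C1D1 if (C1D1 count − L) / L ≥ 0.50, that is, if the C1D1 count is at least 1.5 × L. This is the one scheduled count taken on entospletinib before any antibody.

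C1D1 is not a scheduled response assessment. A progression call then would need an unscheduled assessment, which section 11.2.1 permits when progression is clinically suspected. Table 9, footnote D, ties scheduled response assessment to the CT scans. Through cycle 12 these fall at C4D1, C7D1 and C10D1, all after obinutuzumab has started. Sections 2.3.2.1 and 2.3.4 describe extensive B-cell depletion with that antibody, so an egress-driven rise of this size is less plausible at those visits. It is not excluded: by C10D1 the last antibody dose (C6D1) is 4 × 28 = 112 days past.

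**Step 3: what a progression call does.**

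- Sections 5.4 and 5.6: treatment and study participation end. Section 5.5 reserves the further 12 months of disease assessment for patients who stop for reasons other than progression.
- EFS (sections 1.2 and 13.2.2): recurrence of disease is an event, but the definition does not say that the section 11.2.1 list is how recurrence is judged. An effect is possible, not certain.
- Primary CR endpoint (section 13.2.1): CR has its own lymphocyte criterion (below 4 × 10⁹/L) and does not use the progression list. The only route is removal before a later CR could be seen.

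**Step 4: size.** An estimate needs the frequency of isolated rises of 50% or more on this regimen, and the share of such cases in which the assessor would follow the list. The documents give neither.

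**The case against.** The strongest reply is that the paragraph directly above the list already is the on-entospletinib exception. It names the drug, gives the reason and ends categorically. It is not confined to PR, since PR is handled in its own sentence. The section says that modified IWCLL criteria apply, and this paragraph is the visible modification. On that reading the bullet is a generic item left uncleaned, and an investigator would have to call progression against an explicit instruction. Most of this stands: the paragraph probably governs. It does not remove the defect, because the list is self-contained, needs only one item and does not point back. Nor does preferring the paragraph settle the period after entospletinib stops.

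Several stronger readings are tempting, and the documents do not support them.

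- A reader might infer that the plan has no exception at all for patients on drug. It has one; it is not carried into the list.
- A reader might count every scheduled blood draw on entospletinib as a chance of a false progression call: 4 in cycle 1, 5 in cycles 2–6 and 6 in cycles 7–12, so 15. Scheduled response assessment follows the CTs, not the counts, and all but the C1D1 draw come after antibody has begun.
- A reader might price the problem at 1/17 = 5.9 or 1/20 = 5.0 percentage points of ORR. That is the weight of any single patient, not a measure of this defect.
- A reader might think that a cycle 1 progression call followed by replacement (section 5.1.2) leaves the efficacy denominator open. Sections 11.0 and 13.3 keep anyone who received a dose in the efficacy-evaluable set.
- A reader might add that the 50% rise has no stated reference value. The section relies on a cited guideline that may supply one and cannot be seen here, so nothing is claimed on that.

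**Conclusion.** Section 11.2.1 contradicts itself as written. That follows from the text alone and needs no assumption. The consequences are conditional: they require a patient with an isolated rise of 50% or more and an assessor who applies the list rather than the paragraph. Where both occur on drug, the result is one that the protocol's own reasoning calls wrong, and the patient loses treatment and follow-up.

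The damage to inference is limited. The primary CR test is touched only through early removal. EFS and ORR are summarised descriptively (section 13.4.2), with no test attached. This should be corrected because a wrong call matters to the individual patient and the correction is cheap, not because the trial's main conclusion is in doubt.

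**What to change.** Make two wording changes in section 11.2.1.

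1. Qualify the lymphocyte item in the Progressive Disease list: an isolated lymphocyte rise while the patient is on entospletinib is not progressive disease unless another progression criterion is also met.
2. Limit the sentence that tells assessors to ignore the count to the on-entospletinib period, so that the lymphocyte criterion applies only after entospletinib has been stopped. Progressive Disease After Treatment then imports the qualified item and needs no separate edit.

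Qualifying the item is better than deleting it: deletion would leave no lymphocyte criterion for relapse once entospletinib has stopped.

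The cost is a protocol revision through the usual committee and IRB approval (section 12.5), with any matching text on the response case report form brought into line. No assessments are added, and the sample size and decision rule do not change.

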Patients with HCL must be intolerant of or not candidates for purine analog-based therapy, or failed to achieve response (CR or PR) or relapsed within 2 years of such therapy, AND meet the standard treatment initiation criteria (ANC $\leq 1000/\mu\text{L}$, Hgb $\leq 10 \text{ g/dL}$, platelet count $\leq 100,000/\mu\text{L}$).

Patients with indolent lymphoma (FL, LPL, MZL) and patients with B-cell prolymphocytic leukemia must have an indication for treatment in the opinion of the investigator.

Patients with MCL and patients with CLL in Richter's transformation should have previously received or not be candidates for high dose chemotherapy/autologous stem cell transplant.

3.1.4 For diseases other than CLL, LPL, and HCL, presence of radiographically measurable lymphadenopathy or extra-nodal lymphoid malignancy (defined as the presence of ≥ 1 lesion that measures ≥ 2.0 cm in the longest dimension [LD] and ≥ 1.0 cm in the longest perpendicular dimension [LPD] as assessed by CT or MRI). For LPL, measurable disease will be defined as serum monoclonal IgM $> 0.5 \text{ g/dL}$ or meeting at least 1 of the recommendations from the Second International Workshop on LPL for requiring treatment (Appendix E).

3.1.4 Patients must have ECOG performance status ≤ 2 (Refer to Appendix D).

3.1.5 Patients must have organ function as defined below:

- i) direct bilirubin $\leq 2 \times$ institutional ULN (unless due to known Gilbert's syndrome or compensated hemolysis directly attributable to CLL)
- ii) AST or ALT less than $2.5 \times$ institutional ULN
- iii) estimated CrCL using the Cockcroft-Gault equation $\geq 50 \text{ mL/min}$ (see Appendix B).
- iv) platelets $\geq 50,000/\text{mm}^3$ independent of transfusion support, with no active bleeding, and absolute neutrophil count (ANC) $\geq 1000/\text{mm}^3$, unless due to disease involvement in the bone marrow.

3.1.6 Ability to understand and the willingness to sign a written informed consent document.

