Adverse events assessment	X	X	X
, Weight	X	X	X
Vital signs	X	X	X
ECOG performance status	X	X	X
Physical examination	X	X	X
Hematology	X	X	X
Chemistry	X	X	
CT neck, chest, abdomen and pelvis (with contrast when clinically acceptable)^A	X^B (C4D1 or \leq72 h prior)	X^B (C7D1 and C10D1 or \leq72 h prior)	C18D1 and C24D1
Assessment of B-cell depletion		X (C7D1)	
Biomarker blood sample		X (C7D1)	
Bone marrow aspirate and biopsy (includes biomarker aspirate)^C		X	X
Overall response assessment^D	X	X	X^B

KEY:

^AIn subjects with NHL (FL, MZL, MCL) – PET-CT scans *may* be performed in place of CT scans at screening, during the study and at follow-up. However, the same modality should be used for each individual patient during the study.

^BIn subjects with LPL, CT scans on C4D1, C10D1 and during follow-up will be performed only if lymphadenopathy is present at screening, or if new lymphadenopathy develops during scheduled CT scans on C7D1 or the EOT visit.

^CIf radiographic and laboratory findings suggest that CR has been obtained, a bone marrow aspirate/biopsy should be obtained to confirm CR between 1 and 3 months after the corresponding CT, accompanied by a biomarker sample (10 mL aspirate) – see 9.0, Correlative studies

^DOverall response assessment should be performed when CTs or PET-CTs are performed

^ESubjects may continue entospletinib monotherapy beyond C12.

Table 10. End of Treatment and Follow-up prior to study closure

Visit/Cycle	EOT ^F	Follow up ^F	
Cycle Day	8 weeks after last dose of study drug	Every 3 months for the first year following EOT	Every 6 months for EFS thereafter
Study Windows	+/- 7 days	+/- 7 days	+/- 2 months
Medical history	X		
Concomitant medication (s)	X		
Adverse events assessment	X		
Height, weight	X		
Vital signs	X	X	
ECOG performance status	X	X	
Physical examination	X	X	X
MRD assessment, peripheral blood	X		
Bone marrow aspirate and biopsy; includes biomarker aspirate (all patients)	X^A		
Hematology	X	X	X
Chemistry	X	X	
Serum immunoglobulins	X		
CT neck, chest, abdomen and pelvis (with contrast when clinically acceptable)^B	X	X^{C,D}	
Overall response assessment^E	X	X	
Event-free survival assessment		X	X

KEY:

^AAn optional bone marrow aspirate/biopsy should be obtained between 1 and 3 months after End of Treatment visit, accompanied by MRD assessment and a biomarker aspirate. Exception: patients who underwent a bone marrow biopsy to obtain CR confirmation after 6 cycles of therapy will not undergo EOT bone marrow biopsy

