11.2 Criteria for Response

11.2.1. Subjects with CLL/SLL

Modified IWCLL guidelines [41] will be used to measure response in CLL/SLL subjects.

ORR for CLL/SLL subjects is defined as CR, CRi, nPR and PR, PD and SD. Subjects will be assessed for response at the end of treatment. If there is a clinical suspicion for progression, disease assessment may be performed at any time.

Complete Remission (CR)

Requires all of the following:

- Peripheral blood lymphocytes (evaluated by blood and differential count) below $4 \times 10^9/L$
- Absence of significant lymphadenopathy (eg, lymph nodes >1.5 cm in diameter) by physical examination and imaging, if baseline scans were abnormal
- No hepatomegaly or splenomegaly by physical examination and imaging, if baseline scans were normal
- Absence of constitutional symptoms (B symptoms)
- Blood counts must have the following findings:
 - a) Neutrophils $> 1.5 \times 10^9/L$ without need for exogenous growth factors
 - b) Platelets $> 100 \times 10^9/L$ without need for exogenous growth factors
 - c) Hemoglobin > 11.0 g/dL without red blood cell transfusion or need for exogenous erythropoietin
- Bone marrow aspirate and biopsy must have the following findings:
 - a) Normocellular for age
 - b) Less than 30% of nucleated cells being lymphocytes
 - c) No B-lymphoid nodules (confirmed by IHC)

Complete Response with Incomplete Marrow Recovery (CRi)

Subjects who fulfill all the criteria for a CR but who have a hypocellular marrow and persistent anemia or thrombocytopenia or neutropenia unrelated to CLL but secondary to drug toxicity. If the marrow is hypocellular, a repeat determination should be performed after 4 weeks, or when peripheral blood counts have recovered.

Nodular Partial Response (nPR)

Subjects who fulfill all the criteria for CR but who have bone marrow evidence of B-lymphoid nodules by IHC.

Partial Remission (PR)

Blood count should show at least one of the following results:

- Neutrophils more than $1.5 \times 10^9/L$ without need for exogenous growth factors
- Platelet counts $> 100 \times 10^9/L$ or 50% improvement over baseline without need for exogenous growth factors
- Hemoglobin > 11.0 g/dL or 50% improvement over baseline without requiring red blood cell transfusions or exogenous erythropoietin

AND two of the following three criteria should be met:

- Decrease in number of blood lymphocytes by 50% or more from the value before therapy

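### The post-treatment progression criteria for CLL/SLL contain a platelet sub-item with the threshold 500 and no unit, which is met by noise on one reading and adds nothing on the other

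*Combined protocol and SAP*

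**What the plan says.** The part of Section 11.2.1 headed Progressive Disease After Treatment opens with "Includes at least one of the following". It has two top-level items. The first imports the general progression criteria. The second is "The progression of any cytopenia (unrelated to autoimmune cytopenia) which occurs at least 3 months after treatment as documented by", followed by three sub-items joined by OR:

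- a haemoglobin item, with units in both g/L and g/dL;
- "a decrease of platelet counts by more than 500", with no unit;
- "a decrease of platelet counts by more than 50% or to less than" 100 x 10^9/L, with the equivalent 100 000/µL printed beside it.

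The document states platelet counts in both conventions. Eligibility (Section 3.1) is per mm³, which is the same as per µL, and the CR criteria (Section 11.2.1) use 10^9/L. Nothing says which applies to the 500.

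Blood counts in follow-up are scheduled in Table 10 (Section 10.5) "Every 3 months for the first year following EOT", and in Section 11.1 "every 3 months for the first 12 months, and every 4-6 months thereafter until disease progression or death".

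**The concern.** Any one sub-item is enough to document progression, so the complete platelet item on the next line does not override the one before it. A threshold of 500 is not usable in either unit that the document employs. Per µL it lies far inside ordinary count-to-count variation. In 10^9/L it exceeds any normal or low count.

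Three things could be affected. Disease progression is a ground for removal from study (Section 5.6), so a false progression could end observation before a true event is seen. EFS (Section 13.2.2) ends at objective recurrence, new therapy or death, and Section 11.2.1 is where progression in CLL/SLL is defined. Disease status at follow-up assessments would change as well. With 17 to 20 Phase II patients (Section 13.5), a few spurious events would visibly move a Kaplan-Meier curve.

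**Working it through.** **Inputs from the document.** The threshold of 500, the adjacent platelet item and the OR structure come from Section 11.2.1. The four first-year follow-up counts come from Table 10. The End of Treatment visit is about 2 months after the last cycle (Section 10.2.1) and the first follow-up visit is 3 months later, at about 2 + 3 = 5 months. All four visits therefore fall beyond the 3-month condition.

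**Assumptions, not in the document.** The patient is stable, with normally distributed counts, a mean of 100,000 to 250,000/µL, a within-person coefficient of variation (CV) of 2% to 10%, and one reference count.

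**Step 1: the printed unit equivalence.** 100 x 10^9/L divided by 10^6 µL per L gives 100,000/µL, which agrees with the document.

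**Step 2: the per-µL reading, size of the threshold.** 500/50,000 = 1.0%; 500/100,000 = 0.5%; 500/150,000 = 0.33%; 500/250,000 = 0.2%.

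**Step 3: the per-µL reading, two counts.** P(fall > 500) = 1 − Φ(500 / (√2 × CV × mean)). For a CV of 5% and a mean of 150,000 this is 1 − Φ(500/10,607) = 1 − Φ(0.047) = 0.481. Over the whole grid it runs from 0.43 to 0.49.

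**Step 4: the per-µL reading, at least one such fall in four counts against one reference** (simulation, 400,000 patients per cell).

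| CV | mean 100,000 | mean 150,000 | mean 250,000 |
|---|---|---|---|
| 2% | 0.738 | 0.759 | 0.776 |
| 5% | 0.776 | 0.784 | 0.791 |
| 10% | 0.789 | 0.792 | 0.796 |

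The ceiling is 4/5 = 0.80: with a threshold of zero, the reference is the lowest of five exchangeable counts with probability 1/5. The result depends little on the assumed CV because 500 is so close to zero.

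**Step 5: the complete item on the same assumptions.** A fall of more than 50% occurs in at most 0.002% of stable patients over four counts. The limit of 100 x 10^9/L depends on where the patient sits:

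- At a mean of 150,000 and a CV of 10%, the limit is (150,000 − 100,000)/15,000 = 3.33 SD away. One count falls below it with probability 0.0004, and at least one of four with probability 1 − (1 − 0.0004)^4, about 0.002.
- At a mean of exactly 100,000, half of all counts fall below it, and at least one of four does with probability 1 − 0.5^4 = 0.94. There the 500 line can add at most 1 − 0.94 = 0.06.

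The 500 line therefore changes classification mainly in patients whose counts sit well above 100,000/µL.

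**Step 6: the 10^9/L reading.** A fall of more than 500 needs a reference above 500 x 10^9/L. Between 500 and 1000, such a fall is already more than 50% of the reference, so the complete item is met anyway. The line adds something only when the reference exceeds 1000 x 10^9/L, which has no place in a cytopenia criterion.

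**The case against.** **It may be a typing or reading error.** The line has the same opening words as the next item, ends in a comma and is followed by a detached OR. It could be a false start of that item, or a 50% rendered as 500 when the PDF was read. This stands as a real possibility, and the source must be checked. It does not rescue the line: if it is a fragment, nothing is lost by removing it.

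**The criterion is gated.** The platelet lines sit under progression of a cytopenia that is not autoimmune and occurs at least 3 months after treatment. The simulated patients are stable and not shown to be cytopenic. This stands as a limit on size. It does not cure the defect, because the 500 line is itself listed as what documents the progression, and no repeat count is required.

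**The reach into EFS is narrower than it looks.** The EFS definition does not cite this sub-item. Section 13.2.2 censors EFS when entospletinib is stopped for other reasons, patients who benefit may continue entospletinib beyond cycle 12 (Section 10.2), and study closure ends follow-up. Against this, Sections 5.5 and 10.3 continue EFS follow-up after treatment. The number of patients exposed is therefore uncertain, but not shown to be zero.

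**A reader might infer that most off-treatment patients will be declared progressed.** The documents do not support that. It would require the per-µL reading, applied literally, to patients accepted as having a progressing cytopenia.

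**Conclusion.** The point holds in a limited form. Section 11.2.1 contains a unitless platelet sub-item that can on its own document post-treatment progression and has no workable meaning in either unit. On the per-µL reading roughly 3 in 4 or more stable patients would show such a fall over four quarterly counts. This rests on an assumed CV of 2% to 10% and mean counts of 100,000 to 250,000/µL, and is an upper illustration rather than an expected rate of false progression. On the 10^9/L reading the line is inert at normal and low counts; calling it impossible is strictly true only for reference counts up to 500 x 10^9/L.

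The exposure is confined to progression status in follow-up, removal from study, and EFS in patients who are off treatment and not already censored. EFS is secondary and summarised descriptively (Section 13.4.2). A reader might also infer that the main efficacy result is at risk. It is not: the line plays no part in the CR definition, so the primary endpoint and the 7-of-17 rule are unaffected.

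**What to change.** Check the line against the source document. Then reconcile the two platelet lines in Section 11.2.1 by removing the unitless 500 fragment and its stray OR, so that the one complete, unit-bearing platelet item already in the protocol stands. Before EFS is analysed, re-check any follow-up progression that was recorded on platelet change alone.

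The cost is a one-line edit and a short review of the affected records, if there are any. No new data or procedures are needed.
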